### 12.2 Prior Probabilities

An adaptive design requires prior mean probabilities of efficacy and toxicity at each dose level. These estimates were determined in collaboration by all study investigators based on all available SBRT dose escalation studies, as discussed in [section 1.2.5](#), with particular weight placed on more modern studies using modern radiation techniques. [Table 5](#) outlines the prior mean probabilities for each dose level.

Table 5. Prior mean probabilities of efficacy and toxicity for each dose level of interest.

| Dose Level | PTV2 BED a (a/B = 10) | Prior mean efficacy probability | Prior mean toxicity probability |
|------------|----------------------------------|---------------------------------|---------------------------------|
| 1          | 100 Gy                           | 75%                             | 2%                              |
| 2          | 115.5 Gy                         | 85%                             | 7%                              |
| 3          | 132 Gy                           | 95%                             | 10%                             |

### 12.3 Randomization and Sample Size

A maximum of  $2 \times 24 = 48$  patients will be randomized between two subgroups. Patients in subgroup 1 will receive GC4419 in combination with their assigned RT dose, and patients in subgroup 0 will receive their assigned RT dose and placebo (no GC4419). The randomization will be restricted so that the sample size within each subgroup is exactly 24 patients. The restricted randomization sequence will be constructed prior to trial initiation, and applied by the Statistical

Analyst overseeing the trial treatment and RT dose assignments. An overall accrual rate of approximately 3 patients per month is anticipated, which will give approximately 1.5 patients per month in each subgroup.

## 12.4 Phase I-II Dose Finding Design

Dose-finding will be done using the sequentially adaptive phase I-II Late onset Efficacy-Toxicity (LO-ET) trade-off-based design. For the purpose of dose-finding, as stated in [section 12.1](#):

- **Toxicity** is defined as a grade 3 or 4 gastro-intestinal (GI) toxicity, or death, occurring within 90 days from the start of therapy. For the purpose of dose-finding
- **Efficacy** is defined as stable disease (SD) or better, compared to baseline, as evaluated at day 90 from the start of therapy ([section 10.6.4](#)).

## 12.5 Maximum Sub-sample Size and Cohort Size

[figure not shown]
The same adaptive dose-finding design will be used in each of the two subgroups. Within each subgroup, up to 24 patients will be treated in 8 cohorts of size 3 each. The first cohort will be treated at dose level 1, all successive doses will be chosen by the LO-ET method to maximize the posterior Efficacy-Toxicity trade-off, and an untried dose level (dose level 2) may not be skipped when escalating initially.

## 12.6 Dose Acceptability

For the two LO-ET dose acceptability rules, the upper limit on the probability of Toxicity is 0.15, the minimum probability of Efficacy 0.75, and the decision cut-offs 0.10 will be used or both stopping probability criteria. If the lowest dose level is found to be unacceptable in terms of high toxicity, or if the highest dose level is found to be unacceptable in terms of low efficacy, the trial will be terminated and no dose level will be selected. Accrual will only be paused before proceeding to the highest dose level. Dose level 1 has been safely used previously so there will be no pause in accrual.

## 12.7 Efficacy-Toxicity Trade-Off Contours and Priors

The three equivalent trade-off (pE, pT) probability pairs used for computing the trade-off contours are (0.60, 0), (0.75, 0.15), (1, 0.40). The prior hyper-parameters were computed based on the assumed prior means  $\text{Prob}(\text{Efficacy} \mid \text{dose}) = 0.75, 0.85, 0.95$  and  $\text{Prob}(\text{Toxicity} \mid \text{dose}) = 0.02, 0.07, 0.10$ , respectively, at the three RT dose levels. The prior effective sample size = 1 for the toxicity parameter prior and 1 for the efficacy parameter prior. This is illustrated in [Figure 11](#).

### 12.8 Design Operating Characteristics

Operating characteristics of the design, as conducted within each subgroup, are summarized in [table 6](#) below, based on simulations with 1000 replications per scenario. In the simulations, it is assumed that the times to toxicity and efficacy follow Weibull distributions, the percentage of toxicity (or efficacy) events occurring in the later half of each evaluation interval is 50%, and the accrual rate is 1.5 patients per month. The maximum sample size is 24, with up to 8 cohorts of size 3.

Table 6. Design Operating Characteristics of the current study with 24 patients per arm, 3 dose levels, and accrual rate of 1.5 patients per month, based on simulations with 1000 replications per scenario, assuming toxicity and efficacy follow Weibull distributions.

| Scenario                  |                            | SBRT Dose level |             |             |
|---------------------------|----------------------------|-----------------|-------------|-------------|
|                           |                            | 1               | 2           | 3           |
| 1                         | True toxicity probability  | 0.05            | 0.06        | 0.07 |
|                           | True Response probability  | 0.50            | 0.70        | 0.85 |
|                           | Selection percentage       | 0.20            | 18.5        | 74.9 |
|                           | Average number of patients | 4.7             | 8.3         | 10.1 |
| 2                         | True toxicity probability  | 0.02            | 0.08 | 0.30        |
|                           | True response probability  | 0.60            | 0.80 | 0.90        |
|                           | Selection percentage       | 2.3             | 67.0 | 24.6        |
|                           | Average number of patients | 5.9             | 12.2 | 5.4         |
| 3                         | True toxicity probability  | 0.10     | 0.30        | 0.46        |
|                           | True response probability  | 0.90     | 0.92        | 0.94        |
|                           | Selection percentage       | 80.9     | 9.3         | 0.2         |
|                           | Average number of patients | 15.1     | 4.5         | 0.8         |
| 4
(poor efficacy)      | True toxicity probability  | 0.02            | 0.04        | 0.05        |
|                           | True response probability  | 0.20            | 0.30        | 0.40        |
|                           | Selection percentage       | 0               | 0.1         | 3.4         |
|                           | Average number of patients | 3.5             | 3.7         | 8.9         |
| 5
(excessive toxicity) | True toxicity probability  | 0.35            | 0.45        | 0.60        |
|                           | True response probability  | 0.50            | 0.70        | 0.85        |
|                           | Selection percentage       | 0.1             | 0.4         | 0.1         |
|                           | Average number of patients | 4.9             | 3.5         | 1.1         |

Based on these simulations, should all dose levels in any treatment arm demonstrate > 15% probability of grade 3 or higher toxicity based on prior probabilities and enrolled patients, the study arm will terminate in approximately 6 months with 5, 4 and 1 patients assigned to dose levels 1, 2 and 3, respectively. Should all dose levels in any treatment arm demonstrate < 75 % probability of

stable/responsive disease, the study arm will terminate in approximately 12 months with 4, 4 and 9 patients assigned to dose levels 1, 2 and 3, respectively. Should dose level 3 be the MTD, the study will accrue to completion (approximately 16 months) with 5, 8 and 10 patients assigned to dose levels 1, 2, and 3, respectively. Should dose level 2 be the MTD, the study will accrue to completion (approximately 16 months) with 6, 12 and 5 patients assigned to dose levels 1, 2 and 3 respectively. In this scenario, dose limiting toxicity (DLT) would have to occur in a minimum of 2/5 patients treated at dose level 3. Should dose level 1 be the MTD, the study will accrue to completion (approximately 16 months) with 15, 5 and 1 patients assigned to dose levels 1, 2 and 3 respectively. Again, in this scenario, DLT would have to occur in a minimum of 2/5 patients treated at dose level 2.

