The LO-ET model (Thall et al, 2013; Thall et al, 2012) is rooted in the Bayesian continual reassessment method (CRM), where probabilities of responses for each dose level are continuously assessed as the trial progresses and each patient is enrolled. Instead of requiring all patients to be enrolled and assessment done at the completion of the trial, the “person-time” contributed by each patient for the time they have been enrolled is encompassed in the estimation of response, in addition to any prior data known about the treatment. For example, if two patients have been enrolled and completed a 90 day observational period without toxicity, this will increase the posterior probability of that dose level being “safe.” The LO-ET model takes this model one step farther by utilizing a 2-dimensional continuous reassessment method. In this model, the ideal outcome is estimated as a tradeoff “curve” (Figure 7) between toxicity and efficacy dictated by clinicians, i.e. a 20% toxicity rate is allowable if 75% disease stability/response can be achieved. As dose levels are evaluated with accumulating “person-time,” if at any point it appears the dose level is either too toxic or not efficacious, it is eliminated and no longer accrues patients. This continual reassessment (Figure 8) continues until either all dose levels are eliminated (all dose levels are either too toxic or not efficacious) or a clearly superior arm emerges that meets the prespecified efficacy and toxicity criteria.

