In this novel phase I/II adaptive dose escalation trial (Figure 9) we are addressing two primary questions: Determining the MTD of dose escalated SBRT with and without drug, and comparing efficacy and toxicity of SBRT with and without drug. Our trial design will enroll 48 patients and essentially run two parallel LO-ET models (24 patients per arm) to determine MTD nested within a randomized trial design. Patients are randomized to either “SBRT + Drug” or “SBRT” arms, after which the LO-ET models will run independently in each arm. The flexibility of this model will also allow the “SBRT + Drug” and “SBRT” arms to each continue to trial completion should all dose levels on either arm be eliminated, meaning the above mentioned potential outcomes of identifying an MTD or stopping the arm early due to excess toxicity or efficacy could occur in either the SBRT alone arm or the “Drug” arm. Efficacy threshold will be set at 75% minimum probability of radiographically stable disease or partial/complete response at 90 days. Maximum toxicity threshold will be set at 15% maximum probability of greater than grade 2 gastrointestinal toxicity at 90 days. Prior probabilities of efficacy and toxicity for each dose level are based on a review of all previous available SBRT literature as noted in [section 1.2.2](#) and [1.2.3](#). Further statistical details are available in [section 13.0](#).

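### Table 6, Scenario 3: the selection percentages need a mean of at least 21.7 patients per arm under section 12's rules, but the table reports 20.4

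*Combined protocol and SAP*

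**What the plan says.** Section 12.5 treats up to 24 patients per arm in cohorts of three. Sections 3.4 and 12.3 restrict randomization so that each arm has exactly 24. For the simulations, section 12.8 says: "The maximum sample size is 24, with up to 8 cohorts of size 3".

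Section 12.6 gives two grounds for stopping: the lowest dose is too toxic, or the highest dose is not effective enough. In either case "the trial will be terminated and no dose level will be selected". Section 4.7 likewise closes an arm under the design only when all its dose levels fail the criteria.

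Table 6 is "based on simulations with 1000 replications per scenario". Its Scenario 3 rows, for dose levels 1, 2 and 3, read:

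- "Selection percentage | 80.9 | 9.3 | 0.2"
- "Average number of patients | 15.1 | 4.5 | 0.8"

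The text below the table describes this case: "Should dose level 1 be the MTD, the study will accrue to completion (approximately 16 months) with 15, 5 and 1 patients assigned" to the three levels.

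The background in section 1.2.9 describes stopping differently. Reassessment goes on until all levels are eliminated "or a clearly superior arm emerges that meets the prespecified efficacy and toxicity criteria", and "stopping the arm early due to excess toxicity or efficacy could occur in either the SBRT alone arm" or in the drug arm.

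**The concern.** The two Scenario 3 rows summarise the same simulated trials, so they must agree with each other under the stated stopping rules. If a trial that stops early never selects a dose, then a trial that selects a dose has run to 24 patients. A high selection percentage therefore sets a floor under the mean sample size, and Scenario 3 falls below it.

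Scenario 3 is the only scenario in which dose level 1 is the target and both higher levels (true toxicity 0.30 and 0.46) exceed the 0.15 limit. It is the plan's evidence on how often the design picks an overly toxic level in that situation and how many patients it treats there. Determining the MTD is the primary objective. As printed, a reader cannot rely on both rows, and cannot tell whether the simulated design is the one that section 12 describes.

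**Working it through.** **Inputs.** Maximum 24 per arm, cohort size 3, 1000 replications, accrual 1.5 per month per arm (12.8). Selection percentages and average patient numbers come from Table 6. Early termination means no selection (12.6).

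**Identity.** Let P be the proportion of trials that select a dose. Then

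mean N = 24 × P + (1 − P) × (mean N of non-selecting trials), so mean N ≥ 24 × P.

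A trial that treats 24 patients and still selects nothing only raises the mean, so the floor stands.

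**All five scenarios.** The last column solves the identity for the mean size of a non-selecting trial.

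| Scenario | P | Reported mean N | Floor 24 × P | Implied mean N, non-selecting |
|---|---|---|---|---|
| 1 | 0.936 | 23.1 | 22.46 | 9.9 |
| 2 | 0.939 | 23.5 | 22.54 | 15.8 |
| 3 | 0.904 | 20.4 | 21.70 | −13.5 |
| 4 | 0.035 | 16.1 | 0.84 | 15.8 |
| 5 | 0.006 | 9.5 | 0.14 | 9.4 |

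For Scenario 3, (20.4 − 21.696)/0.096 = −13.5, which is impossible. The other four give plausible values.

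**A slightly stronger floor.** If every non-selecting trial treats at least one cohort, the Scenario 3 mean must be at least 21.696 + 3 × 0.096 = 21.98.

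**Rounding.** Adding 0.05 to each patient average gives at most 20.4 + 0.15 = 20.55. Taking 0.05 points off each percentage gives a floor of 24 × 0.9025 = 21.66. The gap is still 1.1. With 1000 replications the percentages are in fact exact counts (809 + 93 + 2 = 904), so this allowance is generous.

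**Monte Carlo error.** Both rows describe the same replications, so the identity holds exactly within the run.

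**Read in reverse.** A mean of 20.4 lets at most 20.4/24 = 85.0% of trials reach 24, or (20.4 − 3)/21 = 82.9% if each stopped trial has at least 3 patients. With favourable rounding these become 85.6% and 83.6%. The table has 90.4%.

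**Extraction error.** The 12.8 text repeats the averages as 15, 5 and 1, so a misread patient row is unlikely.

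**Duration.** 24/1.5 = 16.0 months reproduces the stated figure for a completed arm, whereas 20.4/1.5 = 13.6 months. This restates the same gap and is not independent evidence.

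**The case against.** The strongest objection is that nothing in section 12 says outright that a dose is selected only at 24 patients. The numbers are given as maxima, section 1.2.9 speaks of ending when a superior arm emerges and of stopping for efficacy, and the design runs on a published program that cannot be inspected here. If the simulation allowed early selection, 20.4 patients with 90.4% selection would be possible and neither row need be wrong.

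The pattern is compatible with that. In Scenario 3, selecting trials would average at most (20.4 − 3 × 0.096)/0.904 = 22.25 patients, a saving of at least 1.75. The same reasoning gives at least (23.1 − 24 × 0.064)/0.936 = 23.04 in Scenario 1 and (23.5 − 24 × 0.061)/0.939 = 23.47 in Scenario 2, so savings of at most 0.96 and 0.53. A larger saving in Scenario 3 is plausible, because dose level 1 has a 0.90 response probability there and the other levels are too toxic. Early selection therefore cannot be excluded.

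It does not clear the plan, however. Section 12 gives no such rule or cut-off, both terminations in 12.6 end without a selection, and 12.8 says this very case runs to full accrual. Under this reading a design rule is missing and the 12.8 sentence is wrong.

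Two further points stand. The duration comparison is weak: 12.8 sets the length of a completed arm beside averages over all trials, and Scenario 4 also departs from mean N/1.5 (10.7 months against a stated 12). The consequence is also limited: even if all 7.5 points came off dose level 1, it would still be selected in 80.9 − 7.5 = 73.4% of trials.

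**Conclusion.** The inconsistency is real and should be fixed. Under section 12's rules the two Scenario 3 rows cannot both be right.

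- If the selection row is right, the patient row is 1.3 to 1.6 patients short (at least 1.1 with rounding in its favour).
- If the patient row is right, the 90.4% total is 5.4 to 7.5 points too high at the printed values. Which dose level's percentage is affected cannot be told.
- If an early-selection rule was simulated, both rows may be right, but section 12 omits the rule and the 12.8 sentence contradicts it.

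The documents do not show which of these applies. Confidence is high in the mismatch itself. It rests on one assumption, taken from 12.6 and 12.8, that an arm which selects a dose has treated 24 patients.

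**What to change.** Check the Scenario 3 simulation output, or rerun it, and correct whichever row is wrong. Bring the matching sentence in 12.8 into line with the result. Print the percentage of trials with no dose selected for every scenario. It can be derived from the existing rows, but showing it makes this check immediate.

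If the simulation did allow an arm to stop early with a dose selected, state that rule and its cut-off in section 12, reconcile it with 1.2.9, 12.6 and 12.8, and remove the statement that this case accrues in full.

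The cost is a check or rerun of one scenario, one added line per scenario in Table 6 and one corrected sentence, plus the rule's text if there was one. Correcting the table changes nothing in trial conduct, stopping cut-offs or randomization.

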## 12.9 Implementation

### 12.9.1 LO-ET Trial Implementation

The Late-Onset Efficacy-Toxicity (LO-ET) design will be implemented using the specialized computer program developed by Jin et al. During trial conduct, application of the statistical design will be carried by [name], a Statistical Analyst in the Department of Biostatistics. This will include (1) randomization of each patient at entry between the two arms, RT+ GC4419 versus RT only, and (2) adaptive dose assignment within each arm using the LO-ET method. Outcome-adaptive dose-finding will be done by inputting the current trial data and running the specialized computer program that implements the LO-ET method. This process will require close interaction between [name] and personnel in the clinic, including repeatedly providing [name] with all dose-outcome data from all previously enrolled patients, including each previous patient's time of Toxicity occurrence or current follow up time without Toxicity, up to the defined 90-day observation interval, and whether efficacy occurred at day 90. Critical variable data (provided within your Study Manual) should be entered into the electronic data capture clinical database in a timely fashion to ensure data is included in the ongoing analysis for SBRT dose level assignments. [name], a Senior Statistical in the Department of Biostatistics, will serve as a backup for [name] in the process of trial conduct. Additional statistical support or input will be provided as required by Drs. [name] and [name]. Details and procedures related to the various safety, efficacy, and correlative analyses will be provided in a formal Statistical Analysis Plan.

### 12.9.2 Secondary Endpoints and Analysis

Secondary outcomes will include progression-free survival (PFS) time and overall response rate in addition to rate of long-term toxicity, surgical resection and rates of R0 and pathologic complete response at resection. Unadjusted distributions of the time-to-event outcomes PFS and OS will be estimated using the method of Kaplan and Meier and their relationship to prognostic covariates and RT cell dose level will be evaluated by Bayesian piecewise exponential survival regression.

Resectability will be assessed at the seven week time point. If a patient goes on to resection, he or she will be categorized as acceptable efficacy. If the patient is deemed unresectable, efficacy will be reassessed at 12 weeks. Toxicity will also be assessed at the 12 week timepoint and descriptive statistics will be generated. If endoscopy exhibits severe toxicity, the patient will be deemed as unacceptable toxicity.

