## **2.0 PRIMARY OBJECTIVES**

### **2.1 Rationale for Primary Objective**

The maximum tolerated dose (MTD) for SBRT using a technique that protects adjacent OAR's is unknown. If dose escalation could be achieved while protecting OAR's, we may be able to deliver ablative doses to the pancreatic tumor and increase local control rates and overall survival rates. Previous studies of radiation in LAPC and BRPC have failed due to inadequate radiation doses, but better prospective studies cannot be designed until the MTD is known. The novel radioprotectant agent, GC4419, may provide additional protection to the gastrointestinal mucosa and modulate the interaction of radiation with tumor tissues, thus resulting in an either higher or lower MTD when given in conjunction with SBRT over SBRT alone. This primary objective was designed to answer this question by allowing parallel MTD selection arms both with and without GC4419.

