### **2.3 Secondary Objectives**

- To evaluate PFS for patients treated with SBRT given in combination with placebo or GC4419
- To evaluate ORR including stable disease and partial/complete response for patients treated with SBRT given in combination with placebo or GC4419
- To compare acute toxicity rate at 90 days for patients treated at the SBRT MTD in combination with placebo or GC4419
- To evaluate late (12 month) toxicity of SBRT in combination with placebo or GC4419

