### 3.4 Randomization and Blinding

Forty eight patients will be randomized 1:1 to Arm A or Arm B. Patients in Arm A will receive GC4419 in combination with their assigned SBRT dose, and patients in Arm B will receive Placebo (PBO) with their assigned SBRT dose. The randomization will be restricted so that the sample size within each arm is exactly 24 patients. The restricted randomization sequence will be constructed prior to trial initiation, and applied by the Trial Statistical Analyst ([name]) overseeing the trial treatment and RT dose assignments. Each patient will be randomized by the MDACC biostatistical analyst maintained for the duration of the study. Patients will be followed by their Patient ID (also known as a CORe Number), assigned by Galera prior to randomization. Operational and system details will be included in the Study Plan and Pharmacy Manual.

Investigators and patients will be blinded to GC4419 or PBO assignment, but not to SBRT dose level assignment. Treatment should remain blinded until the end of the study. Only in the case of an emergency, when knowledge of the investigational product is essential for the clinical management or welfare of the patient, may the investigator unblind a patient's treatment assignment prior to the end of the Post-active Phase. The investigator will, whenever possible, discuss options with the Medical Monitor, on-call physician, or appropriate Galera Therapeutics, Inc./CRO study personnel before unblinding. If the blind is broken for any reason and the investigator is unable to contact Galera Therapeutics, Inc. prior to unblinding, the investigator will notify Galera Therapeutics, Inc./CRO as soon as possible following the unblinding incident without revealing the subject's study treatment assignment, unless the information is important to the safety of patients remaining in the study. In addition, the investigator will record the date and reason for revealing the blinded treatment assignment for that subject in the appropriate section of the CRFs.

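### Section 12.9.2 leaves the randomised arm out of the PFS and OS analysis, so the survival model gives no drug estimate and its dose coefficient could absorb part of a drug effect

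*Combined protocol and SAP*

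**What the plan says.** Section 12.9.2 gives two methods for the survival outcomes. The first is "Unadjusted distributions of the time-to-event outcomes PFS and OS will be estimated using the method of Kaplan and Meier"; no stratification by arm is stated. The second is a model in which "their relationship to prognostic covariates and RT cell dose level will be evaluated by Bayesian piecewise exponential survival regression". The named terms are prognostic covariates and dose level. Treatment arm is not among them, and no other section gives a PFS or OS analysis by arm.

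The aims and the design around that sentence are:

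- Section 3.4: "Forty eight patients will be randomized 1:1 to Arm A or Arm B". Arm is the only randomised factor.
- Section 2.3, PFS objective: "To evaluate PFS for patients treated with SBRT given in combination with placebo or GC4419".
- Section 1.2.9, one of the two primary questions: "comparing efficacy and toxicity of SBRT with and without drug".
- Section 1.2.9, dose assignment: patients are randomised, "after which the LO-ET models will run independently in each arm".
- Section 2.1, expected effect of the drug on dose: "thus resulting in an either higher or lower MTD when given in conjunction with SBRT over SBRT alone".

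Section 12.9.1 defers details of the efficacy analyses to a formal Statistical Analysis Plan, whose text is not among the documents reviewed.

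**The concern.** There are two consequences. First, the only survival model specified does not estimate the contrast the trial randomises. Treatment arm is not a prognostic covariate in ordinary usage, so the wording cannot safely be taken to include it.

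Second, dose level is not randomised. Each arm's LO-ET model chooses dose from that arm's own earlier outcomes. If GC4419 changes toxicity or efficacy, the arms can end with different dose mixes, and arm and dose become correlated. A dose coefficient from pooled data without an arm term could then carry part of the drug effect. That number might be read as a radiation dose effect when the next trial is planned.

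Timing adds weight. Section 12.9.3 provides for one unblinded descriptive efficacy analysis on the first 19 subjects, with results given to investigators. An arm term added after those results are known would be open to challenge as post hoc.

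**Working it through.** **The plan's own figures.** 2 arms × 8 cohorts × 3 = 48 patients, and 24 / 1.5 per month = 16 months, as in Sections 12.3 and 12.8. The documents give no effect size, power or event count for PFS or OS, so there is no survival figure to reproduce.

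**Inputs.** Table 6 average allocations to levels 1/2/3, with the mean level of each:

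- Level 3 best (Scenario 1): 4.7/8.3/10.1; mean (4.7 + 2×8.3 + 3×10.1)/23.1 = 2.23
- Level 2 best (Scenario 2): 5.9/12.2/5.4; mean (5.9 + 2×12.2 + 3×5.4)/23.5 = 1.98
- Level 1 best (Scenario 3): 15.1/4.5/0.8; mean (15.1 + 2×4.5 + 3×0.8)/20.4 = 1.30

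Assumptions not in the documents: exponential PFS, no true dose effect, drug HR of 0.5, 0.65 or 0.8, and follow-up of two control-arm medians.

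**One case by hand.** GC4419 arm as Scenario 1, placebo arm as Scenario 3, drug HR 0.5. With the control median as the time unit, the hazards are 0.6931 (placebo) and 0.3466 (drug). Event probabilities are 1 − 2^(−2) = 0.75 and 1 − 2^(−1) = 0.50. Expected exposure is events divided by hazard.

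- Level 1 (4.7 drug, 15.1 placebo): events 2.35 + 11.33 = 13.68; exposure 6.78 + 16.34 = 23.12; rate 0.592
- Level 3 (10.1 drug, 0.8 placebo): events 5.05 + 0.60 = 5.65; exposure 14.57 + 0.87 = 15.44; rate 0.366
- Apparent level 3 versus level 1 HR: 0.366 / 0.592 = 0.62, although dose does nothing

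**All cases.** Expected-value exponential regression on linear dose level, arm omitted. The table shows the spurious level 3 versus level 1 HR:

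| GC4419 settles at | Placebo settles at | Drug HR 0.5 | 0.65 | 0.8 |
|---|---|---|---|---|
| same dose mix | same dose mix | 1.00 | 1.00 | 1.00 |
| 3 | 2 | 0.86 | 0.91 | 0.95 |
| 2 | 1 | 0.62 | 0.75 | 0.86 |
| 3 | 1 | 0.61 | 0.74 | 0.86 |
| 2 | 3 | 1.18 | 1.11 | 1.05 |
| 1 | 3 | 1.61 | 1.35 | 1.17 |

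With arm added, the dose HR returns to 1.00 and the assumed drug HR is recovered in every row.

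**Size against noise.** In the hand case, SE(log HR) = √(1/5.65 + 1/13.68) = 0.50, and ln 0.62 = −0.48, about one standard error. If every patient had an event, the standard error would be √(1/10.9 + 1/19.8) = 0.38. The largest bias, ln 0.61 = −0.49, would then be 1.3 standard errors.

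**Precision of the arm estimate.** With arm in the model, the standard error of its log HR is about 0.35 to 0.48. Schoenfeld power at two-sided 0.05 with 48 events, from z = (√48 / 2)·|ln HR| − 1.96, is 67%, 32% and 12% for HR 0.5, 0.65 and 0.8.

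**The case against.** The strongest replies are these.

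- **The objective can still be met.** A reader might infer that the plan cannot address PFS at all. The documents do not support that. The PFS objective asks only to evaluate, whereas acute toxicity has the comparative verb: "To compare acute toxicity rate at 90 days for patients treated at the SBRT MTD in combination with placebo or GC4419". Kaplan-Meier curves by arm would meet the PFS objective. The criticism that stands is that neither the curves nor the model is specified by arm.
- **Details are deferred.** The SAP promised in Section 12.9.1 may include arm, and Section 12.9.3 implies that the final efficacy analysis is unblinded. This lowers certainty about what will be done. But Section 12.9.2 does not merely stay silent: it lists the model terms, and a SAP faithful to that list would repeat the omission.
- **The regression may be meant within each arm.** Sections 12.5 and 12.8 are framed by subgroup. Fitted within arm, the dose coefficient could not be confounded by arm. The text does not settle this, and that model would still give no drug estimate.
- **Leakage is conditional.** A reader might infer that any drug effect will appear as a dose effect. It will not if the dose mixes match. Otherwise the leakage is partial and can run in either direction.
- **The illustration mixes sources.** Table 6 allocations come from scenarios with their own response rates (0.50/0.70/0.85 in Scenario 1, 0.90/0.92/0.94 in Scenario 3). These conflict with a beneficial drug in the Scenario 1 arm and with no dose effect. The allocations show how far dose mixes can diverge; they do not forecast the bias.

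**Conclusion.** The omission is in the text and should be corrected. As written, the PFS/OS regression gives no drug estimate, and a pooled dose coefficient is not protected against confounding by arm.

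Under the stated assumptions, the spurious level 3 versus level 1 HR runs from none with equal dose mixes, through 0.86 to 0.95 (GC4419 at level 3, placebo at level 2), to 0.61 to 0.86 (level 3 and level 1). It is 1.17 to 1.61 when that last pairing is reversed, so a beneficial drug could make a higher dose look harmful. These biases are no more than about 1.0 to 1.3 standard errors in a trial of this size. They would distort a descriptive estimate rather than produce a firm false conclusion.

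MTD selection is unaffected. Whether the regression is pooled, and whether the SAP already includes arm, cannot be determined from the documents.

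**What to change.** Amend Section 12.9.2 and carry the change into the SAP:

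1. Give Kaplan-Meier curves for PFS and OS by randomised arm.
2. Fit the piecewise exponential regression with randomised arm, RT dose level and a listed set of prognostic covariates, and state the priors.
3. Report the posterior of the arm HR both without and with dose adjustment. The unadjusted HR is the total effect, including any benefit gained through a different dose; the adjusted HR removes that path. Label both as descriptive.
4. Interpret the dose effect only from the model that includes arm.
5. Treat any arm-by-dose term as exploratory at most. With divergent arms, a cell may hold about one patient (0.8 at level 3 in Scenario 3), and the prior would dominate.
6. Delete the stray word *cell* from the description of RT dose level.

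The cost is a short text change and one model term. No new data and no change to dose-finding are needed. The date of the change relative to the 19-subject interim results should be recorded.
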